### **12.2 Sample Size Justification**

Based on a small pilot study in 2020-2021, sensitivity of lollipop swabs compared to NP was found to be 88%. As we will now be including both asymptomatic and symptomatic individuals, we anticipate the

sensitivity of the lollipop swab to drop to approximately 80%. With a Type I error rate of 5% and a power of 90%, our calculated sample size is 206.

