## 3.0 STUDY SUMMARY

### 3.1 Synopsis

Full Title	The utility of "lollipop" oral swabs in the diagnosis of COVID-19 in an inpatient setting
Short Title	Inpatient COVID-19 Lollipop Study
Protocol Number	2023-0290
ClinicalTrials.gov Identifier & Summary	NCT ID pending. This study is being done to see if collecting saliva samples with a "lollipop" collection method works as well as nasal samples for COVID-19 PCR testing.

Number of Site(s)	UW-Madison will be the only site enrolling subjects.
Main Inclusion Criteria	
 
• Individuals at least 4 years of age
 
• Admitted to a hospital
 
• Verified COVID-19 according to positive NP PCR test criteria
 
• Enroll within 47 hours of the diagnostic NP swab; lollipop swab collected within 48 hours of the diagnostic NP swab
 

Main Exclusion Criteria	
 
• Unable to suck on a swab
 
• Previous participation in this study
 
• Require translation services for medical care
 

Objective(s)	
Primary Objective
 
 
• To determine the performance characteristics of oral lollipop swabs compared to NP swabs for diagnosing COVID-19 via PCR molecular testing.
 
 
Secondary Objectives
 
 
• To identify clinical characteristics of patients when there are discordant results for NP and oral lollipop test results.
 

Endpoints	
Primary Endpoint
 
 
• Tabulated results from NP vs. lollipop swab-based PCR COVID-19 tests.
 
 
Secondary Endpoints
 
 
• Correlation of clinical characteristics to participants with discordant test results
 

Study Design	This is a prospective quantitative study evaluating the utility of a novel method of saliva collection for COVID-19 testing.
FDA Regulatory Overview	
-
 
The investigational swab and associated COVID-19 PCR test are FDA regulated and involve an IDE-exempt in vitro diagnostic device.

Study Device	The lollipop collection swab and the lollipop swab processing procedure are both investigational.
Total Number of Subjects	Up to 225 subjects will be enrolled.

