## 6.0 STUDY OBJECTIVES AND ENDPOINTS

Objectives	Endpoints
Primary To determine the performance characteristics of oral lollipop swabs compared to NP swabs for diagnosing COVID-19 via PCR molecular testing.	Tabulated results from NP vs. lollipop swab-based PCR COVID-19 tests.
Secondary To identify clinical characteristics of patients when there are discordant results for NP and oral lollipop test results.	Correlation of clinical characteristics to participants with discordant test results

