## **12.0 STUDY ANALYSIS**

### **12.1 Statistical Hypotheses**

- Primary Efficacy Endpoint(s):**

- For participants who have had COVID-19 symptoms for <5 days, the sensitivity of lollipop swab-based PCR COVID-19 testing is non-inferior to the sensitivity of NP swab-based PCR COVID-19 testing.

- Secondary Efficacy Endpoint(s):**

- For participants who have had COVID-19 symptoms for  $\geq 5$  days, the sensitivity of lollipop swab-based PCR testing is inferior by 50% to the sensitivity of NP swab-based PCR COVID-19 testing.
- For participants who are asymptomatic, the sensitivity of lollipop swab-based PCR testing is inferior by 50% to the sensitivity of NP swab-based PCR COVID-19 testing.

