### **12.4 Statistical Methods**

Sensitivity and specificity of the lollipop swabs will be calculated.

The primary variable is binary (positive or negative). A separate subgroup analysis of sensitivity/specificity of lollipop swabs will be calculated for asymptomatic, symptomatic (<7 days), and symptomatic (>7 days) individuals.

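### The 90% power and n = 206 in section 12.2 are for whole-cohort sensitivity and do not apply to the primary hypothesis in 12.1 (<5-day non-inferiority), which has no margin and no planned analysis

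*Combined protocol and SAP*

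**What the plan says.** All references are to the combined protocol and SAP.

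- **12.1 Statistical Hypotheses.** The primary hypothesis is "For participants who have had COVID-19 symptoms for <5 days, the sensitivity of lollipop swab-based PCR COVID-19 testing is non-inferior" to that of NP-based PCR. No margin is given. The only numerical contrast in 12.1, inferiority by 50%, belongs to the secondary hypotheses (symptoms for 5 days or more, and asymptomatic participants).
- **12.2 Sample Size Justification.** A small pilot found a sensitivity of 88% against NP. "As we will now be including both asymptomatic and symptomatic individuals", the plan expects the "sensitivity of the lollipop swab to drop to approximately 80" per cent. It then states "With a Type I error rate of 5% and a power of 90%, our calculated sample size is 206". No test, null value or sidedness is named.
- **12.4 Statistical Methods.** "Sensitivity and specificity of the lollipop swabs will be calculated". The subgroups are "asymptomatic, symptomatic (<7 days), and symptomatic (>7 days) individuals". No test, confidence interval or decision rule appears.
- **6.0 and 3.1.** The primary objective is "To determine the performance characteristics of oral lollipop swabs compared to NP swabs for diagnosing COVID-19 via PCR molecular testing", and the endpoint is "Tabulated results from NP vs. lollipop swab-based PCR COVID-19 tests". Neither is limited by symptom duration or mentions non-inferiority.
- **8.1, Inclusion Criterion 5.** Every participant must already have a positive NP PCR.

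**The concern.** The sample size and the primary hypothesis concern different populations. The 80% in 12.2 is chosen because asymptomatic participants are included. The primary hypothesis leaves them out, and 12.1 gives them a secondary hypothesis of their own. The power statement therefore cannot describe the primary hypothesis, whatever test or margin was intended.

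The rest of the plan does not fill the gap. With NP sensitivity at 100% by construction, any negative lollipop swab puts the lollipop below NP, and only a margin says how far below is acceptable. If 12.1 governs, its hypothesis has no stated power, no decision rule and no planned analysis, so the verdict could be settled by choosing a margin after the results are seen. If whole-cohort estimation governs, as 6.0, 3.1 and 12.4 suggest, then 12.1 declares a primary hypothesis that the study was neither sized nor planned to test.

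**Working it through.** **Inputs from the documents:** pilot sensitivity 88%, expected sensitivity 80%, Type I error 5%, power 90%, n = 206 (all 12.2); enrolment cap 225 (3.1, 7.1). **Not in the documents:** the margin, the sidedness, the expected number with symptoms <5 days, and the sensitivity in that group.

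**1. Reproducing 206.** One-sample test of a proportion, normal approximation, null p0 = 0.88, alternative p1 = 0.80, two-sided 5%:

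n = [1.96·√(0.88·0.12) + 1.2816·√(0.80·0.20)]² / 0.08² = (0.6369 + 0.5126)² / 0.0064 = 206.47

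This matches 206. The exact test at n = 206 rejects at 171 or fewer positives and has power 88.0%. The one-sided version gives 171.3. Reversing the roles (null 80%, true 88%) gives 225.2 two-sided and 180.4 one-sided. The source of 206 is therefore inferred: a test of whether whole-cohort sensitivity differs from the pilot value. It is not a non-inferiority test and it uses all participants.

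**2. What the 12.1 hypothesis would need.** With NP at 100%, non-inferiority becomes a one-sample test of H0: p ≤ 1 − margin. The illustration assumes n = 103 (half of 206) and an exact one-sided 2.5% test.

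| Margin (points) | Null | Positives needed of 103 | Power if true sensitivity is 88% |
|---|---|---|---|
| 15 | 85% | 95 | 12% |
| 20 | 80% | 91 | 53% |
| 25 | 75% | 87 | 89% |
| 30 | 70% | 82 | 99.5% |

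Any count from 82 (82/103 = 79.6%) to 94 (94/103 = 91.3%) passes at 30 points and fails at 15.

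**3. Sensitivity to the other assumptions,** at a 20-point margin:

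- n = 103, true sensitivity 84%, 88%, 90%, 95%: power 14%, 53%, 77%, 99.8%.
- True sensitivity 88%, with 206, 103 or 69 participants <5 days: power 85%, 53%, 40%.
- n = 103, true sensitivity 88%, one-sided 5% in place of 2.5%: power 65%.

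**4. Precision if whole-cohort estimation is primary.** Exact (Clopper-Pearson) 95% intervals: 165/206 gives 74.0% to 85.3%; 180/225 gives 74.2% to 85.0%.

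**The case against.** The strongest reply is that this is a small, single-visit, minimal-risk diagnostic study whose objective, endpoint and synopsis all point to estimating sensitivity. The data for a <5-day estimate will be collected, since symptom duration is recorded (7.1), and 12.4 does not forbid further subgroups. A broad objective can sit beside a narrower hypothesis. The power figures above are all conditional on assumptions: at 88% true sensitivity and n = 103, power is 89% or more for margins of 25 points or wider, so they do not show that the study is underpowered.

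Much of that is fair. The <5-day sensitivity can be computed; what is absent is a planned analysis and a rule for judging it. The illustration shows dependence on unstated inputs, not a shortfall. The whole-cohort estimate with an interval remains interpretable. None of this gives the primary hypothesis a margin or a power, and none of it reconciles the 5-day cut in 12.1 with the 7-day cut in 12.4.

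A second reply is that disclosure may not be enough. At a 20-point margin and 88% true sensitivity, 90% power needs 226 participants <5 days (the 225.2 above, rounded up), against a cap of 225 for everyone. That stands as a warning: keeping <5-day non-inferiority as primary may mean accepting power below 90%.

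**Conclusion.** The concern holds and should be fixed before results are known. Followed as written, the plan has no means of deciding its stated primary hypothesis, and the 90% power in 12.2 does not apply to it. This conclusion rests on the text alone: different populations, no margin, no test, and day cuts that disagree. The arithmetic of 206 is not in dispute.

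The size of the effect can only be illustrated. Under the assumed 103 participants and one-sided 2.5% exact test, observed sensitivities from 79.6% to 91.3%, a range that includes the plan's own 80% and 88%, could be declared non-inferior or not depending on whether the margin is 30 or 15 points. A whole-cohort sensitivity with its interval stays sound; a claim of non-inferiority at 90% power would not be.

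**What to change.** 1. State which question is primary: whole-cohort sensitivity, or non-inferiority in participants with symptoms <5 days.
2. In 12.2, name the test, null value and sidedness behind 206, and say that the 90% power does not apply to the <5-day non-inferiority hypothesis.
3. If <5-day non-inferiority stays primary, state before results are known the margin and its reason, a one-sample test or exact confidence interval of lollipop sensitivity against 100% minus the margin, and the expected <5-day count. Report the resulting power or interval width even if power falls below 90%.
4. If whole-cohort estimation is primary, reword 12.1 to match and give the expected precision, for example the 165/206 or 180/225 interval above.
5. Use one symptom-duration cut in 12.1 and 12.4, so that the group in the hypothesis is the group analysed.

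The cost is protocol wording only: no extra participants or procedures. The sponsor must commit in advance to a primary question, a single day cut and, if non-inferiority is kept, a margin. The power stated for a <5-day hypothesis may then look less favourable than 90%.

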### **12.3 Subject Population(s) for Analysis**

Protocol-compliant Population: all participants who provided a lollipop swab that was successfully resulted and complied with the protocol sufficiently to ensure that the data would be likely to represent the effects of the study intervention according to the underlying scientific model.

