## 7.0 STUDY DESIGN

### 7.1 General Design

The Inpatient COVID-19 Lollipop Study is a prospective, single-center study to determine if oral lollipop swabs provide an adequate/optimum sample for diagnosing COVID-19. A total of up to 225 COVID-positive inpatients ages 4 years and older will be enrolled at one study sites. Subject accrual will occur over 6 months with the total duration of the study expected to be 12 months.

Eligible subjects will complete 1 visit that will last approximately 30 minutes. After the study team obtains informed consent and assent, if applicable, the study team will provide verbal instructions and supervise participants as they suck on a flocked swab for 20 seconds. The sample will be labeled with the study ID code and date of sample acquisition, and the result (positive or negative) of the lollipop swab will be compared to the NP swab results in the participant's medical record. Clinical information including symptoms, duration of symptoms, known past COVID-19 infections, known COVID-19 household contacts within 90 days, and COVID-19 immunization status will be assessed via conversation with the participant and review of the electronic medical record. Laboratory information including the cycle threshold of the NP sample will be collected. Each participant will be classified as having either symptomatic or asymptomatic infection. The electronic medical record will be reviewed for medical record number, birthdate, and the above clinical information regarding COVID-19. The sample will be sent to the Wisconsin Veterinary Diagnostic Lab (WVDL) for performance of the PCR for SARS-CoV-2. The specimens will be discarded in the lab after the sample has been processed.

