## 8.7 Early Termination and Withdrawal

Subjects are free to withdraw from participation in the study at any time upon request.

The Principal Investigator (PI) may discontinue or withdraw a subject from the study for the following reasons at his/her discretion:

- Subject non-compliance with study requirements (e.g., unwilling or unable to suck on swab)
- If any clinical adverse event (AE), laboratory abnormality, or other medical condition or situation occurs such that continued participation in the study would not be in the best interest of the subject
- If the subject is no longer an appropriate candidate for participation

Subjects who provide verbal informed consent/assent but do not provide a lollipop swab that can be successfully resulted will not be replaced. Subjects who provide verbal informed consent/assent and provide a lollipop swab that can be successfully resulted, then subsequently withdraw, or are withdrawn or discontinued from the study, will not be replaced.

The study team will attempt to obtain the following information from subjects following early termination or withdrawal: self-reported reason for withdrawal.

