## 9.3 Study Intervention Compliance

Immediately after each study visit, the study team member will complete a Reportable Event Form that asks about protocol deviations, adverse events, participant complaints, and/or any other potentially reportable events that may have occurred. A participant's data will be included in analyses if their lollipop saliva sample is successfully resulted.

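### Sensitivity is planned only among lollipop swabs that gave a result, with no count of those that did not, so it cannot alone show whether the swab is an adequate sample

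*Combined protocol and SAP*

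**What the plan says.** All references are to the combined protocol and SAP.

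- **Analysis set.** Section 12.3 defines a single population: "all participants who provided a lollipop swab that was successfully resulted" and who also "complied with the protocol sufficiently to ensure that the data would be likely to represent the effects of the study intervention". Section 9.3 says that a participant's "data will be included in analyses if their lollipop saliva sample is successfully resulted", with no compliance condition.
- **Outcome.** Section 12.4 makes the primary variable binary and plans only sensitivity and specificity, overall and by symptom subgroup. The endpoint in section 6.0 is a tabulation of NP against lollipop results.
- **Swabs without a result.** Section 8.7 foresees them: consented people who "do not provide a lollipop swab that can be successfully resulted will not be replaced". No section plans a count, a rate or an outcome category for them.
- **Nearest general provisions.** Section 11.1.1 requires missing data on the forms to be explained. Section 12.6 rules out imputation and refers to National Research Council guidance.
- **Aim.** Section 7.1 states the purpose as "to determine if oral lollipop swabs provide an adequate/optimum sample for diagnosing COVID-19". The formal primary objective in section 6.0 is worded differently, as performance characteristics compared with NP swabs.

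**The concern.** Two different questions bear on whether a sampling method is adequate: how often a collected sample gives a result, and how often that result is positive in people known to be infected. The plan estimates only the second. If s is the sensitivity among resulted swabs, the reported figure is s whether no swabs fail or many do.

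A reader choosing between sampling methods could take the reported sensitivity as the chance that a collected lollipop swab detects the infection. It is that chance only if no collected swab fails. With no planned count, the reader cannot convert one figure into the other.

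**Working it through.** **Inputs.** Anticipated sensitivity 80% and pilot sensitivity 88%, both from section 12.2. Calculated sample size 206, at 5% type I error and 90% power, also from section 12.2. Enrolment of up to 225, from sections 3.1 and 7.1. The no-result rate f is not given, so it is treated below as an assumed range.

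**The plan's own figure.** The plan names no formula for 206. A two-sided one-sample test of 0.80 against 0.88 fits:

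n = [1.960 × √(0.88 × 0.12) + 1.282 × √(0.80 × 0.20)]² / 0.08² = (0.6369 + 0.5126)² / 0.0064 = 206.5.

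Power under that test is 89.9% with 206 resulted swabs and 92.0% with 225. The point here is therefore what the estimate means, not how many swabs there are.

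**Gap between the two quantities.** Let N swabs be collected and k give no result, so that f = k/N. Positives number s(N − k).

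- Planned figure: s(N − k)/(N − k) = s.
- Detection per collected swab: s(N − k)/N = s(1 − f).
- Gap: s − s(1 − f) = s × f.

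With N = 225 and s as close to 80% as whole counts allow (exact Clopper–Pearson 95% intervals):

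| No result, k (f) | Resulted only | All collected, no result = not detected | Gap (points) |
|---|---|---|---|
| 1 (0.4%) | 179/224 = 79.9% | 179/225 = 79.6% | 0.4 |
| 5 (2.2%) | 176/220 = 80.0% (74.1–85.1) | 176/225 = 78.2% (72.3–83.4) | 1.8 |
| 10 (4.4%) | 172/215 = 80.0% (74.0–85.1) | 172/225 = 76.4% (70.3–81.8) | 3.6 |
| 19 (8.4%) | 165/206 = 80.1% (74.0–85.3) | 165/225 = 73.3% (67.0–79.0) | 6.8 |

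At s = 88% the gaps are 0.4, 2.0, 3.9 and 7.4 points. The top value, 19, is 225 − 206. It is used only as a convenient end to the range.

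**Effect of cause.** Take k = 10 at s = 80%. If 5 of the 10 are transport, storage or laboratory losses and are left out, the figure is 172/220 = 78.2% (72.1–83.5), against 76.4% when all 10 count as not detected.

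**Direction.** The gap is positive by construction, because the comparison figure scores every no-result swab as not detected. The true status of a lost swab is unknown. If all 10 lost swabs would have been positive, the figure would be (172 + 10)/225 = 80.9%, above the planned 80.0%.

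**The case against.** The best defence is that sensitivity among valid results is a recognised measure, and that the formal objective in section 6.0 asks for performance characteristics, which sensitivity supplies. That stands, and it is why the planned estimate should remain primary. The adequacy wording appears only in the design description in section 7.1.

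The number of failures is also partly recoverable. Section 10.2.3 makes a saliva sample a condition of enrolment, so enrolled minus analysed gives an upper bound. That bound mixes no-result swabs with compliance exclusions. Section 11.1.1 concerns data forms, not a reported rate. What the guidance cited in section 12.6 would require cannot be seen from the documents.

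The documents point both ways on whether laboratory failures belong to the lollipop. Section 9.1.3.2 says the assay is run as for standard-of-care samples, and section 9.1.4.1 describes ordinary delivery and cold storage. Section 3.1 calls the processing procedure investigational. Neither treatment is clearly right, so both should be shown.

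Three stronger readings are tempting, and the documents support none of them:

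- **That leaving these swabs out can only favour the lollipop.** This is true only relative to a figure that counts them as not detected, as the working shows.
- **That the 19 places between 206 and 225 are an allowance for failed swabs.** The documents do not explain that margin.
- **That the <5-day hypothesis or the power is undermined.** Nothing here shows that.

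**Conclusion.** The point holds in a limited form and is worth acting on. The plan restricts its only analysis to resulted swabs and plans no count of the rest, so the reported sensitivity says nothing about how often a collected swab fails. It cannot by itself answer the adequacy question in section 7.1.

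The size depends on a failure rate that the documents do not give. At s = 80% and 225 sampled, the gap is under 2 points for 5 failures or fewer and 6.8 points at the assumed top of the range. If failures are rare the effect is minor, but without the count nobody can tell which case applies.

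Two wording points are secondary. The section 12.3 compliance clause does not say that exclusions are decided without sight of the lollipop result, although section 9.3 has deviations recorded straight after the visit. Section 10.2.3 requires a sample for enrolment, whereas section 10.3 places the sampling visit after enrolment and section 8.7 treats people without a resultable swab as subjects. These blur the denominator but do not carry the point.

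**What to change.** Keep the resulted-only estimate as primary and make these additions:

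1. **Count and cause.** Report the number, percentage and reason for every collected swab without a result. Separate collection or invalid-assay failures from transport, storage or laboratory losses. Record the reason as it arises, in a field completed when the laboratory reports. The section 9.3 form is filled in right after the visit, and section 7.1 has specimens discarded after processing.
2. **Supplementary estimate.** In sections 12.3 and 12.4, prespecify an estimate over all eligible participants who gave a saliva sample (section 10.2.3), without the section 12.3 compliance exclusions. Show it in two versions: (a) all no-result swabs counted as not detected; (b) transport, storage or laboratory losses left out, the others still counted as not detected. State in section 12.6 that this is a defined outcome category, not imputation.
3. **Limit of the comparison.** State that NP failures cannot be observed, because entry requires a positive NP PCR (section 8.1). The supplementary figure is therefore not like-for-like with NP.
4. **Secondary wording.** Decide the section 12.3 compliance exclusions without sight of the lollipop result, and reconcile section 10.2.3 with sections 10.3 and 8.7 so that the denominator is clear.

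The cost is a few wording changes, one data field and one table. The second figure will be somewhat less favourable to the lollipop. The sample size does not change.

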### **10.3.1 Study Visit**

Study visits will occur in a private location, such as the participant’s hospital room, during their inpatient stay at AFCH or University Hospital. Study team members will adhere to the University Hospital’s personal protective equipment (PPE) requirements. After verbal consent/assent is collected and documented in REDCap, the study team will collect basic information about participants, including their name, date of birth, sex, race and ethnicity. If participants are younger than 18 years old, the study team will collect their parent or guardian’s name. The study team will also collect information from participants or their parent/legal guardian verbally and from the participant’s medical record. The information will be relevant to their COVID-19 symptoms and diagnosis, as well as their vaccination status. A detailed list of data points can be found in the Data Collection Sheet. The study team will record this information directly in the study’s SMPH REDCap project. Once a study team member has collected this information, they will guide the participant through the lollipop swab collection. The lollipop swab is obtained by sucking on a swab for 20 seconds in the same way that one would suck on a lollipop. The study procedures will take approximately 15-30 minutes to complete.

A study team member will transport the lollipop swab to the WVDL as soon as possible. The WVDL will provide the study team with the COVID-19 PCR results.

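### Sections 9.3 and 12.3 define different analysis sets, and the undefined compliance condition in 12.3 leaves room for result-dependent exclusions that would raise sensitivity

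*Combined protocol and SAP*

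**What the plan says.** Two sections of the combined protocol and SAP state who is analysed.

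- Section 9.3 (Study Intervention Compliance): "A participant's data will be included in analyses if their lollipop saliva sample is successfully resulted". A result is sufficient.
- Section 12.3 (Subject Population(s) for Analysis) names one population, called protocol-compliant. It requires a resulted swab and, in addition, that the participant "complied with the protocol sufficiently to ensure that the data would be likely to represent the effects of the study intervention".

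Section 12.3 does not say what counts as sufficient, which deviations disqualify a swab, who decides, when, or whether that person is masked to the lollipop result. No analysis of all resulted swabs is planned alongside it.

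Other sections bear on how the condition could be applied:

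- Inclusion criterion 5 (section 8.1) admits only patients with a positive NP PCR.
- Under section 7.1 the study team supervises the collection. Under section 10.3.1 it also gets the outcome: "The WVDL will provide the study team with the COVID-19 PCR results".
- Section 9.3 has the team complete a Reportable Event Form, which covers protocol deviations, directly after each visit.
- Section 8.7 allows the principal investigator to withdraw a participant for non-compliance, and it foresees withdrawal after a swab that can be resulted has been given.

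**The concern.** A swab that has a result but came from an imperfectly compliant participant is in the analysis under 9.3 and may be out under 12.3. The two rules therefore give different denominators for the study's main estimate, and no text says which governs.

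The discretion in 12.3 also matters because of the design. Since every participant is NP-positive, each negative lollipop swab counts as a false negative, and anyone holding the result can see that. A miss invites a search for a reason, such as recent eating or drinking. A positive swab collected in the same way does not. Section 8.3 asks participants not to eat or drink just before collection but sets no interval, so the same facts could be read either way.

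Sensitivity is true positives divided by true positives plus false negatives. Removing a false negative shrinks the denominator and leaves the numerator alone. Exclusions that fall more heavily on negatives therefore push the estimate up. The point concerns swabs that have a result, not swabs that failed to produce one.

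**Working it through.** **Inputs from the documents.** Section 12.2 gives a pilot value ("sensitivity of lollipop swabs compared to NP was found to be 88" per cent), an anticipated value ("sensitivity of the lollipop swab to drop to approximately 80" per cent) and the size: "With a Type I error rate of 5% and a power of 90%, our calculated sample size is 206". The synopsis caps enrolment: "Up to 225 subjects will be enrolled". No section gives a rate of compliance exclusions, so every exclusion figure below is an assumption.

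**The plan's own figure.** A one-sample test of a proportion, null 0.88, alternative 0.80, two-sided 5%, power 90%:

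n = [(1.960 × √(0.88 × 0.12) + 1.282 × √(0.80 × 0.20)) / 0.08]² = 206.5

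This matches 206 to rounding. The present point does not alter it; 206 and 80% serve only as a base for the scenarios.

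**The two rules side by side.**

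| Resulted swab | 9.3 | 12.3 |
|---|---|---|
| Compliance not in question | In | In |
| Compliance in question | In | In or out, by an unstated judgement |

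**Base case under the 9.3 rule.** At 80% of 206 there are 165 positives and 41 negatives: 165/206 = 80.1% (Wilson 95% CI 74.1 to 85.0). At the enrolment cap, 180/225 = 80.0% (74.3 to 84.7).

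**Scenarios as exclusion fractions.** Let S be the true sensitivity, and let a and b be the fractions of positives and negatives excluded. The estimate becomes S(1 − a) / [S(1 − a) + (1 − S)(1 − b)]. With S = 0.80:

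- a = 10%, b = 10%: 0.72 / (0.72 + 0.18) = 80.0%, no bias.
- a = 5%, b = 20%: 0.76 / (0.76 + 0.16) = 82.6%.
- a = 5%, b = 30%: 0.76 / (0.76 + 0.14) = 84.4%.

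**Scenarios as counts, dropping negatives only, from 165/206.**

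| Negatives dropped | Share of the 41 negatives | Share of all 206 | Sensitivity (Wilson 95% CI) |
|---|---|---|---|
| 0 | 0% | 0% | 165/206 = 80.1% (74.1 to 85.0) |
| 5 | 12% | 2.4% | 165/201 = 82.1% (76.2 to 86.8) |
| 10 | 24% | 4.9% | 165/196 = 84.2% (78.4 to 88.6) |
| 20 | 49% | 9.7% | 165/186 = 88.7% (83.4 to 92.5) |

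The last row is an extreme case: it discards about half of all negatives and no positives. At 225 the pattern is similar, with 10 negatives dropped giving 180/215 = 83.7% and 20 giving 180/205 = 87.8%.

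**Reach of these figures.** They cover all participants. The primary hypothesis in section 12.1, that lollipop sensitivity "is non-inferior to the sensitivity of NP swab-based PCR COVID-19 testing", is limited to participants with symptoms for under 5 days. The documents give neither the size of that subset nor an expected sensitivity for it, so the effect there cannot be quantified.

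**The case against.** The strongest reply is that the plan already has a safeguard. Deviations go on a form straight after the visit, when the swab has still to be taken to the laboratory and tested, so they should normally be on record before any result exists. This stands in part. It limits the scope for finding deviations afterwards. It does not settle which recorded deviations exclude a swab, because no text connects the form to 12.3 or lists disqualifying deviations.

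Second, a reader might infer that compliance will be judged after the result is known. The documents do not say so. No section gives the timing or names the assessor. What they support is narrower: the 12.3 condition applies to swabs that have a result, no earlier cut-off is set, and no masking is stated, so nothing prevents an informed judgement.

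Third, a compliant set can be defended. Section 7.1 asks whether the swab gives an adequate or optimum sample under supervision, and the procedure is one short staff-supervised collection. Section 5.4, however, promotes collection at home without a provider, and there imperfect technique is part of performance. The choice of target is arguable, which is a reason to report both sets and to state which is primary.

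Fourth, some possible grounds for exclusion are weak. Section 9.1.4.1 sets no delivery deadline and allows cold storage, so slow transport is not clearly a deviation. Inability to suck on a swab is already an exclusion criterion. Both points narrow the range of plausible exclusions but do not remove the open-ended condition.

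**Conclusion.** The conflict between 9.3 and 12.3 is certain from the text, as is the absence of any definition of sufficient compliance. Upward bias in sensitivity is possible, not shown. It requires exclusions to fall more on negatives than on positives, and the documents give no exclusion rate.

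Under the assumed scenarios the shift runs from nil (equal exclusion), through about 2 to 4 points (82.6% to 84.4%), to 8.6 points in the extreme case (88.7% against 80.1%). The 82.6% scenario lies inside the base interval of 74.1 to 85.0. A reader might take the extreme case, which reaches the pilot's 88%, as the expected result; nothing in the documents supports that.

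This should be fixed before data are analysed. It does not by itself invalidate the design, and it leaves the sample size calculation unchanged.

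**What to change.** In section 12.3:

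1. Define the primary analysis set as all eligible participants with a successfully resulted lollipop swab, so that it agrees with 9.3. Eligibility, including the collection window in inclusion criterion 6, should be checked from recorded facts without reference to the lollipop result.
2. Keep the protocol-compliant set as a sensitivity analysis only. List the disqualifying deviations in advance. Judge them from the Reportable Event Form, either before the WVDL result is released or by someone blind to it, and name who decides.
3. Report the number excluded and the reasons, separately for lollipop-positive and lollipop-negative swabs.

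The cost is a change of wording in 12.3 and a short list of deviations. The form already exists and is already completed at the right time. The sensitivity estimate may be slightly less favourable than one from a compliant set.
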